9.9. Safety Analyses

All adverse events will be recorded throughout the entire study period, whether they are considered to be related to the study procedures or not. Signs and symptoms of each AE will be described in detail: date of event, description of event, severity, relationship to study procedures, action taken and outcome. Adverse events will be collected as spontaneously reported by the subjects.

Adverse events will be coded using MedDRA v22.1. The number of any adverse events and the number and percentage of subjects reporting each type of adverse event will be presented by Preferred Term. Multiple occurrences of the same event reported by the same subject will be counted only once.

Adverse event summaries (number of events and incidence) will be presented for:

- All adverse events
- Serious adverse events (SAEs)
- Study procedure related adverse events
- Severe adverse events

Study procedure related events will include those events classified as possibly or definitely related to the study procedure.

The intensity of an AE will be categorized as follows:

- Mild: Events that are easily tolerated with no disruption of normal daily activity
- Moderate: Events that cause sufficient discomfort to interfere with daily activity
- Severe: Events that incapacitate and prevent usual activity

Causal relationship assessment to study procedures is required for purposes of reporting AEs. To promote consistency, the following guidelines should be taken into consideration along with good clinical and scientific judgment when determining the relationship of study procedures to an AE:

- Definitely Related: A clinical event, including laboratory test abnormality, occurring in a plausible temporal relationship to the study procedures, and which cannot be explained by concurrent disease or other drugs or chemicals.

- Possibly Related: A clinical event, including laboratory test abnormality, with a reasonable temporal relationship to the study procedures, but which could also be explained by concurrent disease or other drugs or chemicals.
- Unlikely Related: A clinical event, including laboratory test abnormality, with little or no temporal relationship to the study procedures, and which could be explained by concurrent disease or other drugs or chemicals.
- Not Related: A clinical event, including laboratory test abnormality, that has no temporal relationship to the study procedures

Action taken will be defined as:

- None;
- Study procedures interrupted;
- Study procedures stopped

Outcome will be defined as:

- Resolved;
- Ongoing or stabilized and followed by private MD;
- Lost to follow up

9.10. Medication Usage

Prior and concomitant medication usage will be coded using the WHO Drug Dictionary Global (version 01SEP2019) and presented separately in the listings. A prior medication is defined as a medication end date that is more than 30 days prior to the informed consent date. All other medications will be considered concomitant medications.

9.11. Protocol Deviations

Protocol deviations will be presented in the subject listings.

10. Statistical Software

All analyses will be performed with SAS (v9.4 or later) and R (v3.6.0 or later for bootstrap sampling analyses).

11. Changes to Planned Analysis

Due to the COVID-19 pandemic, study enrollment was stopped on March 11, 2020 prior to completing the planned targeted enrollment. All statistical analyses will be performed as planned using all available data. Although the sample size is lower than targeted, the number of subjects enrolled exceeds the required number of subjects to achieve 80% power for both the primary and secondary endpoint hypotheses. For purposes of the subgroup analysis of the primary endpoint by race, the following race categories will be reported: White, Black or African American, Other.

Also, the subject selection sampling scheme for waveform assessment in Section 7.2 has been updated to ensure a roughly equal balance of SR and AF cohort subjects based on the number of subjects enrolled at the time study enrollment was stopped.

12. References

- ¹ Ben Freedman S, Lowres N. Asymptomatic Atrial Fibrillation: The Case for Screening to Prevent Stroke. *JAMA*. 2015 Nov 10;314(18):1911-2. doi: 10.1001/jama.2015.9846.
- ² Moran PS1, Teljeur C, Ryan M, Smith SM. Systematic screening for the detection of atrial fibrillation. *Cochrane Database Syst Rev*. 2016 Jun 3;(6):CD009586. doi: 10.1002/14651858.CD009586.pub3.
- ³ Lloyd-Jones DM1, Wang TJ, Leip EP, Larson MG, Levy D, Vasan RS, D'Agostino RB, Massaro JM, Beiser A, Wolf PA, Benjamin EJ. Lifetime risk for development of atrial fibrillation: the Framingham Heart Study. *Circulation*. 2004 Aug 31;110(9):1042-6. Epub 2004 Aug 16.
- ⁴ Colilla S1, Crow A, Petkun W, Singer DE, Simon T, Liu X. Estimates of current and future incidence and prevalence of atrial fibrillation in the U.S. adult population. *Am J Cardiol*. 2013 Oct 15;112(8):1142-7. doi: 10.1016/j.amjcard.2013.05.063. Epub 2013 Jul 4.
- ⁵ Omboni S1, Verberk WJ2. Opportunistic screening of atrial fibrillation by automatic blood pressure measurement in the community. *BMJ Open*. 2016 Apr 12;6(4):e010745. doi: 10.1136/bmjopen-2015-010745.
- ⁶ O'Neal WT1, Efird JT2, Judd SE3, McClure LA4, Howard VJ5, Howard G3, Soliman EZ6,7. Impact of Awareness and Patterns of Nonhospitalized Atrial Fibrillation on the Risk of Mortality: The Reasons for Geographic And Racial Differences in Stroke (REGARDS) Study. *Clin Cardiol*. 2016 Feb;39(2):103-10. doi: 10.1002/clc.22501. Epub 2016 Feb 16.
- ⁷ Brachmann J1, Morillo CA2, Sanna T2, Di Lazzaro V2, Diener HC2, Bernstein RA2, Rymer M2, Ziegler PD2, Liu S2, Passman RS2. Uncovering Atrial Fibrillation Beyond Short-Term Monitoring in Cryptogenic Stroke Patients: Three-Year Results From the Cryptogenic Stroke and Underlying Atrial Fibrillation Trial. *Circ Arrhythm Electrophysiol*. 2016 Jan;9(1):e003333. doi: 10.1161/CIRCEP.115.003333. presented as both frequency counts and as a percentage.
- ⁸ Evaluation and Reporting of Age-, Race-, and Ethnicity-Specific Data in Medical Device Clinical Studies. FDA Guidance Document. September 12, 2017.

13. Appendix: Schedule of Events

Schedule of Events Matrix

Procedure	Screening	Study Day***
	Before Enrollment	In-Lab
Informed Consent	X	
I/E Criteria Assessment	X	
Medical History including allergies	X	
Demographic information	X	
12-lead ECG	X	X**
Vital Signs	X	
Urine Pregnancy Test*	X	
Wrist/Hand Assessment (Dominant hand, skinfold thickness, wrist circumference, wrist hairiness, tattoos)	X	
Physical Examination (will include at a minimum general appearance, lungs, cardiovascular, head and neck, abdomen, musculoskeletal/extremities, lymph nodes, skin and neurological assessment)	X	
Social History (smoking status, alcohol use, recreational drug use, caffeine intake)	X	
Body Measurements and Assessments (anthropometrics) (height, weight, BMI)	X	
Concomitant Medications	X	X**
Dispense Study Equipment, test set-up, record device ID assigned to subject		X
Record watch series, size, watch material (aluminum, steel, etc.)		X
Record subject choice of wrist for device. Default is left wrist		X
Take baseline resting heart rate		X
Practice taking ECG reading		X
Collect ECG reading with both device and 12-lead ECG - 3 trials		X
Practice exercise trial to determine resistance/speed		X

Collect ECG reading after each exercise trial with both device and 12-lead ECG - 3 trials		X
Detach 12-lead ECG		X
Remove wrist device		X
Transfer data from wrist device to paired smartphones		X
Record Adverse and/or Serious Adverse Events		X
Disposition Status Assessment		X

*For women of child-bearing potential only. A woman will be considered not of child-bearing potential if they are surgically sterile and have provided documentation, or they are ≥ 55 and have not had a cycle for ≥ 2 years.

**Only needed if study day is different from screening day

*** Study Day can be on the same day or different day than the Screening Day.

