7.1. Sample Size

[REDACTED] The sample sizes to achieve 80% power with a one-sided type I error of 0.025 using an exact binomial test are [REDACTED] with no known diagnosis of AF and [REDACTED] with a known diagnosis of AF.

Table 7.1 below presents the expected percent correct associated with the four secondary endpoints 2a, 2b, 2c, and 2d and are summarized below along with the proposed performance goals.

Table 7.1: Sample size determination for four secondary endpoints

[REDACTED] To account for obtaining readable/classifiable waveforms and to ensure enough data is collected from the exercise stage, 168 subjects with no known diagnosis of AF and 400 subjects with a known diagnosis of AF will be enrolled.

[REDACTED] To account for obtaining readable waveforms and to assess waveform equivalence across a

range of heart rates and rhythms, approximately 100 subjects (50 SR; 50 AF) will be randomly selected according to the sampling scheme presented in Section 7.2.

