7.2. Randomization and Blinding

Subjects in this study will not be randomized to any treatment regimens.

Approximately 100 subjects (50 SR; 50 AF) will be randomly selected to assess waveform equivalence of the ECG app to Lead 1 from a 12-Lead ECG. Subjects will be randomly selected using a systematic sampling approach. A number between 1 and 6 will be randomly selected for the AF cohort and then every 6th consecutively enrolled AF subject will be selected at random within each site. Likewise, a number between 1 and 5 will be randomly selected for the SR cohort and then every 5th consecutively enrolled SR subject will be selected at random within each site.

US board-certified cardiologists will be blinded to the subjects' past medical history, stage (resting or exercise) and ECG app classifications during the assessment and adjudication of ECG data.

Cardiac technicians will be blinded to the subjects' past medical history, ECG app classifications, stage (resting or exercise) and origin (ECG app or 12-lead ECG) of the waveform being reviewed during the assessment and adjudication of ECG data.

Adjudicators will be instructed to review ECGs independently and separately of each other and not to confer about diagnoses.

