Because data will be collected from the same subjects at rest and after exercise, a bootstrap approach will be implemented to obtain two-sided 95% confidence intervals for the sensitivity and specificity to account for potential within-subject correlation. Subjects with at least one adjudicated result of AF (for sensitivity), SR (for specificity) and with a classifiable algorithm result (i.e., SR or AF) will be selected at random with replacement and the 2.5th and 97.5th percentiles of the distribution of bootstrap estimates will represent the two-sided 95% confidence bounds. If the lower confidence bounds for both sensitivity and specificity exceed the pre-established performance goal associated with these performance metrics, the null hypothesis will be rejected in favor of the alternative hypothesis. Sensitivity and specificity estimates will also be presented separately for at rest and after exercise measurements along with their corresponding Fisher’s Exact 95% confidence intervals.

As an additional analysis associated with the primary endpoint, the sensitivity and specificity will also be estimated and reported along with their corresponding bootstrap two-sided 95% confidence intervals by including the Inconclusive algorithm classification category in the calculation. More specifically, the sensitivity and specificity for the additional analysis will be estimated as follows:

$$\text{Sensitivity estimate (additional analysis)} = n_{22}/(n_{12} + n_{22}+n_{32})$$

$$\text{Specificity estimate (additional analysis)} = n_{11}/(n_{11} + n_{21}+n_{31})$$

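### Does the SAP's statement that 80% power survived the early stop need to be corrected, given that it counts enrolled rather than analysable subjects?

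*SAP*

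**What the plan says.** SAP 7.1 sets out the sizing in two steps. The first is the calculation: "The sample sizes to achieve 80% power with a one-sided type I error of 0.025 using an exact binomial test are" one number per cohort, both redacted. The second is the enrolment target, which is deliberately larger: "168 subjects with no known diagnosis of AF and 400 subjects with a known diagnosis of AF will be enrolled". The reason given for the increase is this: "To account for obtaining readable/classifiable waveforms and to ensure enough data is collected from the exercise stage".

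SAP 11 reports that "study enrollment was stopped on March 11, 2020 prior to completing the planned targeted enrollment". It acknowledges that the sample is smaller than targeted, keeps all analyses as planned, and adds that "the number of subjects enrolled exceeds the required number of subjects to achieve 80% power for both the primary and secondary endpoint hypotheses". It gives no enrolled or analysable count.

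Three other provisions bear on the point:

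- SAP 8 limits endpoints 1a, 1b and 2a to 2d to subjects with readable paired results. SAP 9.6 and 9.7 use only classifiable algorithm results in the relevant reference category.
- SAP 9.6 rejects the primary null only on a double pass: "If the lower confidence bounds for both sensitivity and specificity exceed the pre-established performance goal" is the condition.
- SAP 9.6 and 9.7 let each subject contribute up to two paired results, one at rest and one after exercise.

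SAP 7.2 also changes the waveform sampling. For the SR cohort, "a number between 1 and 5 will be randomly selected for the SR cohort and then every 5th consecutively enrolled SR subject" is taken within each site, where the protocol (section 3.4) took every third. The AF interval remains six.

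**The concern.** The required numbers in SAP 7.1 come before the allowance for lost strips, so they read as analysable subjects. SAP 11 measures enrolled subjects against them. If enrolment only just cleared the requirement, the loss that the SAP itself expected would take the analysable number below it.

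Two features seem to make this worse. Endpoints 2c and 2d need strips adjudicated at 100 to 150 bpm, so their yield is less certain than that of the pooled primary endpoints. And the primary test needs both sensitivity and specificity to pass, so 80% for each would not be 80% for the pair.

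The sentence is the SAP's only statement about power after the stop. If it is wrong, a missed secondary goal could be read as a device failure in a well-powered test when the test was in fact weak.

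**Working it through.** **Can the stated 80% be reproduced?** No. It needs the required size, the performance goal and the expected rate for each endpoint (all redacted), and the enrolled and classifiable counts (not given). What follows is conditional on assumed inputs.

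**Exact binomial power, one result per subject.** The test is one-sided at 0.025. The critical count r is the smallest with P(X ≥ r | goal) ≤ 0.025, and power is P(X ≥ r | expected rate). For each assumed pair, n is the smallest size from which power stays at or above 0.80 over 30 consecutive sizes.

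| Assumed goal / expected rate | n | Power at n | Power at 0.8n | Power at 0.6n |
|---|---|---|---|---|
| 0.80 / 0.90 | 113 | 0.84 | 0.71 | 0.47 |
| 0.85 / 0.92 | 185 | 0.84 | 0.70 | 0.60 |
| 0.90 / 0.95 | 255 | 0.86 | 0.68 | 0.50 |
| 0.90 / 0.97 | 114 | 0.87 | 0.71 | 0.39 |
| 0.92 / 0.97 | 194 | 0.87 | 0.68 | 0.54 |

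- *No excess over the requirement, 80% analysable:* 0.68 to 0.71.
- *No excess, 60% analysable:* 0.39 to 0.60. Part of that spread is the saw-tooth of the exact test. Averaged over n ± 5, it is 0.49 to 0.57. Nothing in the documents suggests a 60% yield.
- *25% excess, 80% analysable:* 1.25 × 0.8 = 1.00, so the analysable number equals n and power is 0.84 to 0.87.

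The answer turns on the margin by which enrolment exceeded the requirement, which SAP 11 does not give.

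**Two results per subject.** The primary endpoints pool rest and exercise. Take no excess, a 15% loss of subjects, and within-subject correlation ρ. The effective size is 2 × 0.85n / (1 + ρ). Power averaged over ± 5, across the same five pairs:

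| ρ | Power per endpoint |
|---|---|
| 0 | 0.97 to 0.98 |
| 0.3 | 0.91 to 0.92 |
| 0.6 | 0.84 to 0.86 |
| 1 | 0.72 to 0.77 |

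Unless the two results are almost fully dependent, the second recovers what the loss removes.

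**Joint power of the co-primary test.** If each endpoint had exactly 80%, joint power would be 0.80 × 0.80 = 0.64 under independence, with outer limits of 0.80 + 0.80 − 1 = 0.60 and 0.80. A joint 80% needs √0.80 = 0.894 for each. At the sizes n in the first table, joint power is the square of power at n, which is 0.71 to 0.76. SAP 7.1 gives one size per cohort beside redacted text. SAP 7.3 and 9.6 speak of a single primary hypothesis and a single null. The 80% could be per endpoint or joint.

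**The four percent-correct tests together.** 0.80⁴ = 0.41 if independent. SAP 9.7 tests 2a to 2d one by one, with no visible rule that all four must pass, so the plan makes no claim against which to set this figure.

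**What the sampling change implies.** Every 5th SR and every 6th AF subject, with roughly equal yield, implies SR:AF of about 5:6. With fewer than 568 enrolled, AF is below 568 × 6/11 = 309.8, which is 1 − 309.8/400 = 22.5% under target. The matching SR figure is 568 × 5/11 = 258.2, or 54% above its target of 168 (258.2/168 = 1.54). If SR did not pass 168, AF was at most 168 × 6/5 = 201.6. On either reading AF fell well short of 400. But 400 is the inflated target, and a shortfall against it says nothing about the redacted required number.

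**Which strips count for 2c and 2d.** SAP Tables 5.1 and 9.6 define the strata by adjudicated heart rate, not by stage. A resting strip adjudicated AF at 100 to 150 counts towards 2d, so these endpoints do not depend on exercise strips alone.

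**The case for a change.** The strongest case for acting is that the SAP claims 80% for the secondary hypotheses without a single stratum count. The second result per subject helps there much less than for the primary, because rest and exercise are meant to fall in different heart-rate strata. The exercise yield is uncertain as well. The target in SAP 5.2.1.3 is 85% of (220 − age), capped at 150, and the cap applies up to about age 43 (220 − 150/0.85 = 43.5). Subjects aim above the target, and a strip adjudicated over 150 leaves both 2c and 2d, as does one below 100. Correcting the sentence would cost one paragraph.

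Most of this stands as a description. The comparison in SAP 11 is not like with like, the secondary endpoints are the more exposed, and the visible text does not say whether the primary 80% is joint. None of it shows that the 80% is false.

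Nor would the correction give the reader much. Reference-strip counts taken before the algorithm runs would still include Inconclusive and Poor Recording strips, because classifiability is an output of the algorithm. The counts that do matter are already planned: measurement accountability by cohort (SAP 9.3), column totals by rhythm and rate (SAP Table 9.6), and Inconclusive and Poor Recording counts by reference category (SAP 9.8, item 5). Analyses that include Inconclusive results are planned too (SAP 9.6 and 9.7). If a goal is missed, the interval width and its denominator show how much precision there was, more directly than a retrospective power figure would.

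**Conclusion.** The sentence in SAP 11 is loosely worded and, as written, does not by itself establish 80% power. It sets enrolled subjects against a requirement that SAP 7.1 states before its own allowance for loss. Whether power actually fell below 80% cannot be determined. With 80% of subjects analysable and one result each, the assumed pairs give 0.68 to 0.71 with no excess enrolment and 0.84 to 0.87 with a 25% excess. Counting two results per subject pushes the primary endpoints higher still. The goals, expected rates, loss rates, excess and correlations are all assumptions, because the real values are redacted or unreported.

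No change to the plan follows. Recruitment had ended, and the statement enters no estimate, confidence interval, success criterion or type I error. The tables already specified will show the analysable numbers for each endpoint. A power figure restated after the stop would alter no conclusion. A reader should treat the sentence as background and judge any missed goal by its denominator and interval.

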#### **3.4. Randomization and Blinding**

Subjects in this study will not be randomized to any treatment regimens.

Approximately 100 subjects (50 SR; 50 AF) will be randomly selected to assess waveform equivalence of the ECG app to Lead 1 from a 12-Lead ECG. Subjects will be randomly selected using a systematic sampling approach. A number between 1 and 6 will be randomly selected for the AF cohort and then every 6th consecutively enrolled AF subject will be selected at random within each site. Likewise, a number between 1 and 3 will be randomly selected for the SR cohort and then every 3rd consecutively enrolled SR subject will be selected at random within each site.

US board-certified cardiologists will be blinded to the subjects' past medical history, stage (resting or exercise) and ECG app classifications during the assessment and adjudication of ECG data.

Cardiac technicians will be blinded to the subjects' past medical history, ECG app classifications, stage (resting or exercise) and origin (ECG app or 12-lead ECG) of the waveform being reviewed during the assessment and adjudication of ECG data.

Adjudicators will be instructed to review ECGs independently and separately of each other and not to confer about diagnoses.

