7.6. Interim Analyses

There are no interim analyses planned in this study.

8. Analysis Sets

The following analysis sets are defined for this study.

Full Analysis Set (FAS): All subjects who sign informed consent and are enrolled into the study. This analysis set will be used to summarize subject 12-Lead, and ECG app device accountability in addition to demographic and baseline characteristics and safety data. The data for this analysis set will be presented overall and separately for the enrollment cohorts.

Classifiable Analysis Set (CAS): All subjects who have readable paired ECG app and 12-Lead ECG adjudicated results. This analysis set will be used for analyzing the co-primary endpoints (1a, 1b), the four secondary endpoints (2a, 2b, 2c, and 2d) and the additional analyses.

Waveform Assessment Analysis Set (WAAS): Randomly selected subjects with readable paired strips from the ECG app and Lead 1 of the 12-Lead ECG. If 6 consecutive beats for analysis cannot be found in these strips, they will be excluded from further analysis. This analysis set will be used for assessing the clinical waveform accuracy associated with secondary endpoints 2e and 2f.

9. Analysis Approach

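### Does taking every 5th SR subject contradict the planned 50 SR subjects for waveform assessment?

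*SAP*

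**What the plan says.** SAP 7.1 sets enrolment: "168 subjects with no known diagnosis of AF and 400 subjects with a known diagnosis of AF will be enrolled". The same section sets the waveform sample: "approximately 100 subjects (50 SR; 50 AF) will be randomly selected according to the sampling scheme presented in Section 7.2".

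SAP 7.2 gives the scheme. For AF: "A number between 1 and 6 will be randomly selected for the AF cohort and then every 6th consecutively enrolled AF subject". For SR: "a number between 1 and 5 will be randomly selected for the SR cohort and then every 5th consecutively enrolled SR subject". Selection is made within each site. Protocol 3.4 has the same AF interval but a shorter SR interval: "a number between 1 and 3 will be randomly selected for the SR cohort", followed by every 3rd subject.

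SAP 11 (Changes to Planned Analysis) reports that enrolment stopped on 11 March 2020, short of target, because of the pandemic. It says the 7.2 scheme "has been updated to ensure a roughly equal balance of SR and AF cohort subjects based on the number of subjects enrolled" at that point. It adds that "the number of subjects enrolled exceeds the required number of subjects to achieve 80% power for both the primary and secondary endpoint hypotheses". It prints no enrolled count, overall or by cohort.

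**The concern.** Read together, SAP 7.1 and 7.2 seem not to add up. One section promises 50 SR subjects from 168, and the other uses an interval that draws about 34 from 168. The change from 1-in-3 to 1-in-5 also looks backwards: at the planned numbers it moves the sample away from balance, although balance is the stated purpose.

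Two things would be at stake. The waveform hypotheses (2e and 2f) could rest on fewer subjects than stated. And if SR enrolment ran well above 168 while the total fell short of 568, the AF cohort would be well below 400. A single sentence on power covering all endpoints could then hide a shortfall for the AF endpoints (1b, 2b, 2d). That sentence also counts enrolled subjects, whereas 1a, 1b and 2a to 2d are analysed in a set that SAP 8 defines as "All subjects who have readable paired ECG app and 12-Lead ECG adjudicated results".

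**Working it through.** **Inputs.** Planned SR 168 and AF 400 (SAP 7.1), total 568 (Protocol synopsis). Waveform sample about 50 SR and 50 AF (SAP 7.1, 7.2). Intervals: SR 3 in Protocol 3.4 and 5 in SAP 7.2; AF 6 in both. Final enrolment is below target (SAP 11), taken here as a total below 568.

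**Formula.** Expected number selected = cohort size / interval.

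**Step 1. Try to reproduce the stated 50:50 from the planned enrolment.**

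| Scheme | SR | AF | Total |
|---|---|---|---|
| Protocol (1-in-3, 1-in-6) | 168/3 = 56 | 400/6 = 66.7 | 122.7 |
| SAP (1-in-5, 1-in-6) | 168/5 = 33.6 | 400/6 = 66.7 | 100.3 |

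Neither gives 50:50. On a single list, every random start at 1-in-5 gives 33 or 34 SR. Rounding within sites can add at most 0.8 per site, so reaching 50 would need (50 − 33.6)/0.8 = 20.5, that is at least 21 sites, each with the most favourable remainder. The number of sites is not given.

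**Step 2. Ask which enrolment the SAP intervals do fit.** Equal selection requires SR/5 = AF/6, so AF = 1.2 × SR. For 50 of each, SR = 50 × 5 = 250 and AF = 50 × 6 = 300. The total is 550, below 568.

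**Step 3. Check the direction of the change at that enrolment.** With 250 SR and 300 AF, the protocol intervals give 250/3 = 83.3 SR and 300/6 = 50 AF. Changing only the SR interval to 5 gives 50:50. That is the change made, and it serves the purpose SAP 11 states.

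**Step 4. Size of the implied shift.** SR: 250/168 = 1.49, about 49% above plan. AF: 300/400 = 0.75, about 25% below plan. With SR at 250, the total below 568 caps AF at 568 − 250 = 318, which is 20.5% below 400. The sample sizes are approximate, so the cap moves: 45 SR selected implies 225 SR and AF below 343 (14% short); 40 SR selected implies 200 SR and AF below 368 (8% short).

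**Step 5. The other reading: SR stayed at or below 168.** About 34 SR are then selected at most, before site rounding. Equal balance needs AF of 33.6 × 6 = 202, about half its target, and 67.2 selected in all. The intervals for 2e and 2f would be about √(100/67.2) = 1.22 times as wide as with 100 subjects. If a 60:40 AF:SR split still counts as roughly balanced (an assumption), AF is 50.4 × 6 = 302, the total selected is 84, and the ratio is √(100/84) = 1.09.

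**The case for a change.** The strongest case for a change is that SAP 7.1, 7.2 and 11 cannot all be literally true. If SR is near 250, the enrolment figures in 7.1 are out of date and nothing says so. If SR is at or below 168, the scheme does not give 50. The reader needs the cohort counts to see that 1-in-5 follows from enrolment. The sponsor must have had them, and printing them costs almost nothing. The power statement is also hard to accept as one sentence when the required numbers are set per cohort.

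Part of this stands. SAP 11 gives no counts, 7.1 does not mark 168 and 400 as superseded, and the apparent shift in cohort mix has to be inferred. The rest does not lead to a change:

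- The 34-versus-50 comparison applies an interval reset to actual enrolment to a planning target that SAP 11 sets aside.
- The other reading cannot be ruled out, but it fits poorly. Equal balance would put AF near 202 and the sample near 67, while 7.1 and 7.2 both keep about 100.
- A shortfall against 400 is not a shortfall against the number required. SAP 7.1 says 168 and 400 allow for unreadable or unclassifiable recordings and for enough exercise data. The 100 waveform subjects also include an allowance for readability.
- The required numbers and performance goals are redacted, so printed cohort counts would not let a public reader check the power sentence. It also plays no part in any test: success depends on the bootstrap lower bounds.
- SAP 9.2 already reports enrolled, withdrawn and completing subjects by cohort and site, and SAP 9.3 reports ECG measurement accountability by cohort. Both the counts and the gap between enrolled and analysable subjects will be visible there.

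**Conclusion.** No change to the plan follows. The mismatch is real only if the SAP's SR interval is applied to the superseded target of 168. Applied to enrolment near 250 SR and 300 AF, the scheme gives the stated 50:50, the total stays below 568, and the move from 1-in-3 to 1-in-5 does what SAP 11 says it was for. The rule in 7.2 is unambiguous and can be carried out as written. No estimate or test of 1a, 1b or 2a to 2f is shown to be wrong, and no loss of power is shown.

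What remains is a documentation gap, which the planned accountability tables fill: the cohort counts at the stop are not printed, and the targets in 7.1 are not labelled as the initial plan.

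This rests on two assumptions: that falling short of target refers to the total of 568, and that the stated 50:50 approximately describes the sample drawn. If SR in fact stayed at or below 168, the waveform sample would be about 67 to 84 subjects, and the 2e and 2f intervals roughly 1.09 to 1.22 times as wide as at 100. That would cost precision, but it would not invalidate the test.
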